**Secondary Aim: Effects of vitamin D3 and EPA/DHA on incidence rate of recurrent HF hospitalizations.**

**Study design:** Randomized, placebo-controlled, double-blind, 2x2 factorial trial of vitamin D3 and EPA/DHA.

**Hypothesis:** Intervention with either vitamin D3 or EPA/DHA reduces the rate of recurrent HF hospitalization.

**Study subjects:** All 25,871 VITAL participants.

**Statistical model:** We will analyze recurrent HF hospitalizations using the Andersen-Gill model, which allows for varying numbers of events per person with different time between events. It can accommodate correlated observations within individuals by using robust covariance estimates. This method has been found to produce similar results to Poisson regression models allowing for over-dispersion.

**Statistical power:** To estimate the statistical power for recurrent HF hospitalization, we assumed a Poisson distribution with over-dispersion, following Cook et al. Rates of recurrence were based on those seen in the Olmstead County data with 16.5% recurrent hospitalization rate (0.144 per person-year). We will have 80% power to detect 16% reduction in recurrent HF hospitalization (RR=0.84) if we assume an incidence rate of 8.29/1000 person-years and 83% power to detect 19% reduction in recurrent HF hospitalization (RR=0.81) assuming a HF rate of 6.19/1000 person-years. We expect 280 recurrent HF hospitalizations with latter rate.

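### The 280 expected recurrences give about 42% power for a recurrent-hospitalization rate ratio of 0.81, not the stated 83%, and the plan does not show which calculation was used

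*Combined protocol and SAP*

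**What the plan says.** The power paragraph of the Secondary Aim (section 3, Research Design and Methods) makes two claims:

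- at the higher HF rate, "80% power to detect 16% reduction in recurrent HF hospitalization (RR=0.84) if we assume an incidence rate of 8.29/1000 person-years";
- at the lower rate, "83% power to detect 19% reduction in recurrent HF hospitalization (RR=0.81) assuming a HF rate of 6.19/1000 person-years".

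It then states: "We expect 280 recurrent HF hospitalizations with latter rate". The recurrence rate is taken from an external cohort as 0.144 per person-year. For the variance, "we assumed a Poisson distribution with over-dispersion", with a cited methods source, but no over-dispersion value is printed.

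The hypothesis is also worded in terms of recurrence: "Intervention with either vitamin D3 or EPA/DHA reduces the rate of recurrent HF hospitalization". The analysis is an Andersen-Gill model, "which allows for varying numbers of events per person with different time between events", in "All 25,871 VITAL participants". The paragraph does not say whether the first hospitalization counts as an event in that model.

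**The concern.** The aim, the hypothesis, the effect size and the only printed event count all name recurrent hospitalization. Yet 280 events are few for a rate ratio of 0.81.

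The plan's own Table 2 (Primary Aim 1) points the same way. For first HF at 6.19 per 1,000 person-years it lists 72% power at an observed RR of 0.81. The secondary aim claims 83% at the same RR and the same HF rate, while quoting far fewer events and adding over-dispersion. At 8.29 per 1,000, Table 2 reaches 80% at RR 0.82, and the secondary aim claims 80% for the weaker effect of 0.84.

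What is at stake is how a null result would be read. Readers would take it as coming from an analysis with 80–83% power for a 16–19% reduction in recurrences. If recurrences alone carry the comparison, the power for such a reduction is about half that.

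**Working it through.** **Inputs from the plan.** N = 25,871, equal allocation, mean follow-up of 5 years with minimal loss, and HF rates of 6.19 and 8.29 per 1,000 person-years (Primary Aim 1, Statistical power). Recurrence rate 0.144 per person-year, RR 0.81 and 0.84, and 280 recurrences at the lower rate (Secondary Aim).

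**Assumptions.** Two-sided 5%, which is stated for Primary Aim 1 and not restated here. No deaths. The over-dispersion factor φ is not in the plan and is shown over a range.

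**1. Reproduce the 280.** With first-event rate r per person-year:

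- First events = N(1 − exp(−5r)): 788 at 6.19 and 1,050 at 8.29.
- Person-years after the first event = N[5 − (1 − exp(−5r))/r]: 1,981 and 2,644.
- Recurrences = 0.144 × those person-years: 285 and 381.
- First plus recurrent: 1,074 and 1,431, of which about 73% are first events at either rate.

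The 285 is close to the printed 280. So 280 is the whole-trial count of events after the first. It is neither a per-arm count nor a first-plus-recurrent count.

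**2. Power on recurrences alone.** Power = Φ(√(D/(4φ)) × |ln RR| − 1.96). For D = 280 and RR 0.81 with φ = 1: √70 × 0.2107 = 1.763, and Φ(1.763 − 1.96) = 0.42.

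| HF rate, RR | D | Stated | φ = 1 | φ = 1.2 | φ = 1.4 |
|---|---|---|---|---|---|
| 6.19, 0.81 | 280 | 83% | 42% | 36% | 32% |
| 8.29, 0.84 | 381 (derived) | 80% | 40% | 34% | 30% |

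More generous conventions do not close the gap at RR 0.81: a one-sided test gives 55%, and treating 280 as a per-arm count (560 events) gives 70%.

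**3. Events needed and detectable RR, before over-dispersion.**

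- 83% at RR 0.81: 4 × ((1.96 + 0.954)/0.2107)² ≈ 765 events.
- 80% at RR 0.84: 4 × ((1.96 + 0.842)/0.1744)² ≈ 1,033 events.
- RR detectable at 80% power, exp(−2.80 × √(4/D)): about 0.72 with 280 events and 0.75 with 381.

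**4. RR acting on one rate only.** With expected recurrences a (placebo) and b (active), power = Φ(|ln(b/a)|/√(φ(1/a + 1/b)) − 1.96). Whether the RR acts only on the later rate or only on the first-event rate, the counts are about 143 vs 116 (6.19) and 190 vs 160 (8.29). Recurrences fall by about 19% and 16%, as printed, but power at φ = 1 is only 36% to 39%.

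**5. Readings that recover both stated powers.**

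- *(a) First plus recurrent events.* With the formula in step 2, D = 1,074 and 1,431 and φ = 1.4 give 83% and 80%. The exact φ values are 1.40 and 1.39.
- *(b) Recurrences only, with the RR acting on both the first-event rate and the later rate.* Counts are about 143 vs 94 (ratio 0.657) and 190 vs 135 (ratio 0.707). With the formula in step 4 and unrounded counts, φ = 1.2 gives 82% and 80%. Recurrences fall by about 34% and 29%.

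Each reading fits both figures with a single φ, so the documents do not identify which was used.

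**The case against.** The strongest reply is that an Andersen-Gill model in all randomized participants usually counts every hospitalization from randomization, first and later. The stated powers would then belong to total HF hospitalizations, and 83% need not be a miscalculation. One φ fits both powers. The fit does not depend on the first-event counts used above: Table 2's powers imply about 583 and 797 first events, and adding 280 and about 375 (280 × 8.29/6.19) recurrences fits both figures at φ of about 1.13. This is a fair case that (a) is what was run. It also means that the 73% first-event share would be about 68% on Table 2's counts.

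Reading (b) is weaker. The plan's rates imply φ of about 1.47 for recurrences, and (b) then gives about 74% and 72%. The same derivation gives φ of about 1.6 for total events, which lowers (a) to about 77% and 74%. That is a shortfall of about 6 points, not half the stated power.

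Two further points are fair. The event definition and the over-dispersion handling may be in the cited source, which cannot be consulted here. And this is a secondary aim whose sample size was set by the parent trial, so no design decision depends on the sentence.

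None of this makes the sentence correct as written. Under (a), the endpoint named and the only count printed are not those behind the power. A reader who takes the sentence at its word is misled about recurrences.

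**Conclusion.** The concern holds, in conditional form. If RR 0.81 and 0.84 are ratios of recurrent-hospitalization rates, the recurrences expected give about 42% and 40% power against the stated 83% and 80%. Both are upper limits, since over-dispersion above 1 lowers them. This rests on two-sided 5%, a 1:1 split, 5 years of follow-up and no deaths.

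It is not shown that the underlying calculation was wrong. Total events, or an RR acting on both rates, can each recover the stated powers, but each requires the sentence to say something different. The documents do not settle which applies. This should be fixed, in proportion to its place as a secondary aim.

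**What to change.** Restate the power sentence to match the calculation actually used. At each HF rate, give the event count, the over-dispersion factor and where the RR acts. Then:

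- **If total events were used:** name the endpoint as total (first and recurrent) HF hospitalizations and attach the 80% and 83% to it.
- **If the RR acts on both rates:** keep the powers, but state the reduction in recurrent hospitalizations they refer to (about 34% at 6.19 and 29% at 8.29 under the assumptions here).
- **If the RR is the ratio of recurrent-hospitalization rates alone:** replace 83% and 80% with about 42% and 40% before over-dispersion, and give the detectable RR (about 0.72 with 280 events at 80% power).

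The cost is SAP wording and restated figures, with no new data or analyses. The downside is a less favourable or differently labelled power figure.
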